Evaluation of pharmacist interventions in lipid management for secondary prevention

NCT06647238

Document date: October 24, 2024

Lipids Research Protocol

Title: Second Time's the Charm: Evaluation of pharmacist interventions in lipid management for secondary prevention

Principal Investigator: [name], BCACP, CDCES, CPP

Co-Investigators:

[name], MSCR

[name], CDCES, BCPS, CPP, DPLA

[name], CDCES, BCPS, CPP

[name], PharmD

[name], BCACP, CDCES, CPP

[name], BCPS, CPP, CDCES

Background/Significance:

Studies have shown prevention of cardiovascular adverse events is directly proportional to percent reduction in LDL.¹ This evidence explains why LDL targets for secondary prevention have continued to be lowered. Cholesterol guidelines have been updated recently and encourage the use of multiple lipid lowering therapies, in addition to statins, for secondary prevention. However, these novel agents can be expensive and difficult to acquire, making prescribing challenging for providers.

This project aims to utilize a pharmacist to evaluate patients for evidence-based therapy and initiate guideline-directed lipid lowering therapy as indicated.

Study Purpose:

The primary objective of this research project is to compare the effect of pharmacist interventions versus usual care in the implementation of guideline directed lipid lowering therapies for secondary prevention.

Study Design: prospective interventional study

Methods/Data Collection

Patient Identification:

- Internal medicine providers and PharmDs will identify patients who are not meeting LDL goals for secondary prevention and could benefit from pharmacist intervention
- SlicerDicer will be utilized to select patients for the control arm as well as potentially for the intervention arm if referrals alone do not meet the sample size goal

Collected data will be stored on a secure Atrium server and de-identified. Data will be analyzed utilizing REDCap. Data collected via EPIC may include:

- Demographic information (age, gender, race)
- Baseline information (recent lipid panel, Lp(a) history)
- Initial hyperlipidemia treatment
- Relevant lab information (renal function, electrolyte values)
- Other co-morbidities (diabetes, CKD, etc)
- Insurance type
- Follow up appointments
- Other relevant patient information for an appropriate hyperlipidemia treatment recommendation

The study period is expected to be 5 months (anticipated November 2024-March 2025).

Inclusion Criteria:

- Age \geq 18 yo

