- Diagnosis of coronary artery disease
- Most recent LDL value > 55
- PCP at 1 of 6 identified clinics

Exclusion Criteria:

- Patients who are no longer an active patient of one of the internal medicine practices
- Patients whose cholesterol is managed by another practice
- Women of childbearing age/potential
- Patients residing in hospice/LTC facilities
- End-stage liver disease

Practice Sites:

- Kannapolis Internal Medicine
- Concord Internal Medicine
- Ardsley Internal Medicine – Harrisburg

- Atrium Health Primary Care Cabarrus Family Medicine – Locust
- Atrium Health Primary Care Cabarrus Family Medicine - Midland

In-person, initial visit:

- Perform medication reconciliation and adherence assessment
- Assess recent laps in EPIC profile
- Educate patient on background of project (pharmacist lipid intervention), provide information sheet, future steps/plans
- Adjust hyperlipidemia treatment, which is part of the routine clinical practice under the collaborative practice agreement.
 - CPP is a licensure that is obtained from the NC Board of Pharmacy and is renewed yearly; CPPs must complete an additional 20 hours of continuing education each year
 - A CPP has an established collaborative practice agreement (CPA) with a supervising physician that outlines the role of the CPP
 - Each pharmacist working on this project either practice as a CPP or are under the direct supervision of CPP
- Order appropriate lab work
- Arrange follow-up with patient regarding medication changes (phone visit)
 - Follow up visits will be scheduled every 6-8 weeks as needed based on patient-specific needs
 - Once LDL<55 (controlled), no further follow up will be scheduled with PharmD
- Will also plan to check Lp(a) for patients who have never had this lab assessed
 - Will provide information sheet on this lab and what to do if it comes back as elevated

Follow up visits:

- Repeat lipid panel prior to appointment, review results
- Assess adherence and access to recommended therapy
- Discuss therapy adjustments
- Set up next follow up visits

The initial in-person visit, or a follow-up telephonic phone visit may be completed by another embedded pharmacist within one of the clinics included in study due to schedule availability. Members of the PharmD team will be trained and follow the protocol during their visits.

Medications are being adjusted as per the usual care services provided by their PCP office and

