PharmD services that are already in place at each practice. Adjustments to medication regimens, comorbidities, and concurrent medications will be made based on national guidelines and evidence-based recommendations that are already allowable by CPP and per our collaborative practice agreement. Any costs/risk associated with medication changes is no additional risk than if they do not participate in the study and would still be subject to these medication changes if they weren't participating in the study. This study and applicable additional intervention are simply offering additional care services provided by a PharmD for closer follow up and offering patients assistance with access to newer therapeutic options.

Control Group:

Patients meeting inclusion criteria will be pulled from SlicerDicer. Any patients previously referred to the project by their provider will be excluded from the control group. Patients included in the report will then be randomized and chosen for retrospective chart review. The goal will be to include 75 patients in both the intervention and control arms. Investigators will perform retrospective chart review for the study period and record the same data as collected for patients in the intervention arm.

Primary endpoint: patients with LDL within goal (<55) (yes/no)

Secondary endpoints:

- Percent LDL reduction (will use baseline LDL and lowest LDL)
- Medication related problems identified and solved
- Medications initiated or titrated
- Number of patients who were provided assistance with access to medication
- Prevalence of elevated Lp(a)

Data and Safety Monitoring:

Principal investigator and co-investigators will meet monthly to re-evaluate patient enrollment and ensure all investigators are adhering to study protocol.

Statistical Analysis:

Data will be analyzed after de-identification using descriptive statistics or inferential statistics as appropriate and will be collected, organized, and stored through REDcap. T-test will be utilized to compare pharmacist intervention versus usual care on the primary outcome. Descriptive statistics will be utilized to report secondary outcomes.

Feasibility of Project:

The anticipated start date for patient enrollment is November 2024. Statistical analysis will be finalized by April 2025. Anticipate presentations/publication in May or June 2025.

Informed Consent:

Participants will be required to provide signed informed consent prior to inclusion in the study.

References:

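### The no-added-risk sentence is hard to reconcile with the study's objective, and no item in either arm is defined to show lipid drugs stopped or reduced for adverse effects

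*Combined protocol and SAP*

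**What the plan says.** The risk statement stands in the paragraph that follows the visit descriptions and precedes Control Group. It says that "Any costs/risk associated with medication changes is no additional risk than if they do not participate in the study" and gives as the reason that patients "would still be subject to these medication changes if they weren't participating in the study". The sentences before it explain that pharmacist services already operate at each practice and that the changes fall within the existing collaborative practice agreement. The sentence after it describes the study as extra pharmacist care, with tighter follow-up and help in obtaining newer drugs.

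Study Purpose sets the objective: to "compare the effect of pharmacist interventions versus usual care in the implementation of guideline directed lipid lowering therapies for secondary prevention". Background/Significance says the pharmacist will "initiate guideline-directed lipid lowering therapy as indicated". One secondary endpoint is "Medications initiated or titrated".

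Under Data and Safety Monitoring, the investigators "meet monthly to re-evaluate patient enrollment and ensure all investigators are adhering to study protocol". Nothing else is listed there.

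Two further rules matter. Percent LDL reduction is computed from the baseline and the lowest LDL (Secondary endpoints). Pharmacist follow-up is no longer scheduled once LDL is below 55 (In-person, initial visit).

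**The concern.** The risk sentence rests on patients getting the same changes outside the study. The objective, the added services and the drug-change endpoint all point to a service meant to put more therapy in place than usual care does. Where more drugs are started or titrated, more patients are exposed to whatever adverse effects those drugs have, even if each change is one that routine care already allows.

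That would matter less if the plan defined a way to see the consequences, but it does not. At the end the investigators could report how many patients reached LDL below 55 and how many drugs were started. They would have no pre-specified count of how many lipid drugs were stopped or reduced because the patient could not tolerate them. The monthly meeting, under a heading that includes safety, would have no defined safety item before it.

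**Working it through.** No stated figure bears directly on this point. The goal of 75 per arm comes without alpha, power, expected rates or dropout, so it cannot be reproduced, and the point does not depend on it. The main check is textual. The arithmetic only shows what harm data could support at this size.

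**Step 1: risk sentence against the rest of the plan.** The risk sentence compares participating with not participating and says the drug changes would happen either way. The objective compares the pharmacist service with usual care on how far therapy is implemented. Patients already referred to the project are kept out of the control group, so the arms are built to differ in this service. That existing services permit a change does not show that it would occur as often without the study.

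**Step 2: search for a harm item.**

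| Place | What it lists | Harm item named? |
|---|---|---|
| Primary endpoint | LDL below 55, yes or no | No |
| Secondary endpoints | Percent LDL reduction; medication-related problems; drugs started or titrated; access assistance; elevated Lp(a) | No; the second could catch some, but is undefined and framed around problems solved |
| Data list | Demographics, lipids, treatment, renal and electrolyte results, comorbidities, insurance, appointments, and an open item tied to choosing treatment | No |
| Follow up visits | Lipid panel, adherence, access, therapy adjustment | No |
| Data and Safety Monitoring | Enrolment and protocol adherence | No |
| Control Group | The same data as the intervention arm | No, so the gap is in both arms |

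**Step 3: the lowest-LDL rule with the end of follow-up.** Let B be baseline LDL, L the lowest value, and F any later value after a drug is stopped. Recorded reduction = 100 × (B − L)/B. F does not enter, so a rise in LDL after stopping leaves the result unchanged. If L is below 55, no later pharmacist visit is scheduled at which the stop would come to light. The primary endpoint has no stated time point, so the text does not settle whether such a patient still counts as at goal.

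**Step 4: what 75 per arm could support.** All event rates are assumptions, and the denominator is the full arm.

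- Chance of at least one event = 1 − (1 − p)^75. At p = 1% it is 53%, at 2% it is 78%, at 5% it is 98%.
- Upper 95% limit with 0 of 75 events: one-sided 1 − 0.05^(1/75) = 3.9%; two-sided exact 1 − 0.025^(1/75) = 4.8%.
- Power between arms, assuming two-sided alpha of 0.05 and the normal approximation: Φ{[d√n − 1.96√(2p̄(1 − p̄))] / √(p₁(1 − p₁) + p₂(1 − p₂))}, where d = p₂ − p₁ and p̄ is their mean. For 5% versus 10%: (0.433 − 0.730)/0.371 = −0.80, giving 21%. For 5% versus 15% it is 53%; for 5% versus 20% it is 80%.

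A harm item at this size would bound or describe a rate. It would not test a modest difference.

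**Step 5: ascertainment.** Intervention patients have an initial visit and follow-ups every 6 to 8 weeks as needed. November 2024 to March 2025 is 151 days, about 21.6 weeks, so 21.6/8 = 2.7 to 21.6/6 = 3.6: two or three follow-ups at most. Controls have retrospective chart review and no study contact. Identical abstraction would not make the chance of an event being charted equal.

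**The case against.** The strongest defence is context. The surrounding sentences say that the pharmacist services already exist and that every change is allowed under the practice agreement. Read that way, the risk sentence says that a given change is no riskier inside the study than outside it, not that the arms will have equal drug exposure. The next sentence is open about the extra services. This stands in part: the sentence does not call the drugs risk-free, and a reworded version could be accurate. But the stated reason, that patients would have these changes anyway, goes further than that reading needs.

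The endpoint on medication-related problems and the non-exhaustive data list could pick up some side effects. That stands, and it limits the point to harm capture being undefined. A reader might infer that nothing could record harm, or that every event would go unrecorded. The documents do not support that: events may well be in the charts, only not specified for abstraction.

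A reader might also argue that if the risk sentence is true, no difference between arms can be expected. That does not follow. Adherence assessment and help with access could lower LDL with identical prescribing.

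Finally, a harm comparison would be biased by unequal contact and would have low power. Both are true. They are reasons to report it descriptively with the bias stated, not reasons to leave the item undefined.

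**Conclusion.** The point holds as a low-cost improvement in reporting and oversight. The risk sentence needs reconciling with the objective. Neither arm has a defined item for adverse effects, intolerance or discontinuation. The lowest-LDL rule, together with the end of pharmacist follow-up below 55, means that a later stop for side effects would leave the recorded reduction intact with nothing planned to show it. The gap in harm data does not alter the primary comparison.

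The size of the problem cannot be given as a count of events, because the documents supply no intolerance rate. What can be said is what a defined item would add: an upper limit of 4.8% (two-sided) if no event is seen in 75 patients. That assumes complete charting, and the limit widens if only patients with a drug change form the denominator.

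Three stronger readings are not supported. The first is that harms were left out because of the risk sentence; the documents give no reason for the choice of endpoints. The second is that the study can report only benefit; it can show no difference or favour usual care. The third is that the exclusion for "End-stage liver disease" shows a recognised hepatic risk left unmonitored; an exclusion criterion is not a statement of risk, and the laboratory items are part of a non-exhaustive list.

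**What to change.** - Reword the risk sentence to say that each change is of a kind already allowed in routine care, but that the intervention arm may receive more starts and titrations.
- Add one secondary safety item, abstracted from EPIC with the same definition and the same window in both arms: any lipid-lowering drug stopped or reduced for a charted adverse effect, with the reason. Run the window to the end of the study period, so that stops after LDL falls below 55 are included.
- Report counts per arm with exact confidence intervals and no test. State that more frequent pharmacist contact will probably raise recorded events in the intervention arm relative to control.
- Make the intervention-arm events a standing item at the existing monthly meeting.

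The cost is some protocol wording, two or three REDCap fields and a few more minutes per chart for about 150 charts (2 × 75) already due for review. No visit, test or treatment rule changes. The drawbacks are a less favourable risk sentence and a between-arm comparison that unequal ascertainment will limit.

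### The control arm's LDL entry criterion has no index date and the deciding endpoint LDL is unnamed, so a report run late relative to intervention entry would select controls partly on the outcome

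*Combined protocol and SAP*

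**What the plan says.** Everything here is in the combined protocol and SAP.

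- **Entry.** Inclusion Criteria requires "Most recent LDL value > 55", with no date or look-back window.
- **Control source.** Under Control Group, "Patients meeting inclusion criteria will be pulled from SlicerDicer". The run date of the report is not given. Then "Patients included in the report will then be randomized and chosen for retrospective chart review", which is random sampling from the list.
- **Timing clue.** "Any patients previously referred to the project by their provider will be excluded from the control group". So at least some referrals come before the list.
- **Control data.** "Investigators will perform retrospective chart review for the study period and record the same data as collected for patients in the intervention arm". The study period is 5 months, anticipated as November 2024 to March 2025.
- **Endpoint.** "Primary endpoint: patients with LDL within goal (<55) (yes/no"). It does not say whether the last, the lowest or any LDL decides, or within what window. Only a secondary endpoint names its values: "Percent LDL reduction (will use baseline LDL and lowest LDL").
- **Repeat testing.** The Follow up visits section, which covers pharmacist visits, has "Repeat lipid panel prior to appointment, review results". No repeat panel is scheduled for controls.
- **Size and test.** The target is 75 patients in each arm, with a t-test on the primary outcome. Alpha, sidedness and expected goal rates are not stated.

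**The concern.** An intervention patient's eligibility is naturally judged at the initial visit, before the pharmacist acts. A control has no visit, so only a written date can fix when the LDL is judged, and none is written.

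Take a control whose LDL falls from 80 to 50 under usual care. If the report is run after that result, the most recent LDL is 50 and the patient fails entry. Charts are chosen only from the report, so this success is never reviewed. An intervention patient with the same course qualified at 80 and counts as a success. The two arms are then selected by different rules on the outcome variable, and a difference can appear with no pharmacist effect. The same can happen if LDLs dated before the run are counted as control outcomes.

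Using 55 both for entry and for success is not a fault in itself. The missing date is.

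**Working it through.** **Inputs.** From the protocol: 75 per arm and a t-test. Assumed, because the documents give no figures: no true effect, two-sided 0.05, the same true goal rate q in both arms, and a fraction f of would-be control successes screened out by the report. The target of 75 has no stated inputs, so there is no figure of the plan's own to reproduce.

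**Method.** Exact binomial enumeration of the pooled two-sample t-test on 0/1 data, 148 degrees of freedom.

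**Step 1: only controls are screened.** This assumes that every intervention patient qualifies at the start of the period. The intervention rate is q and the control rate is

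q(1 − f) / (1 − qf).

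For q = 10%, f = 50%: 0.05 / 0.95 = 5.3%. False-positive rates:

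| q | f = 0 | 25% | 50% | 80% | 100% |
|---|---|---|---|---|---|
| 2% | 3% | 3% | 3% | 5% | 6% |
| 5% | 5% | 6% | 11% | 27% | 52% |
| 10% | 5% | 8% | 20% | 55% | 95% |
| 20% | 5% | 10% | 33% | 84% | about 100% |

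The f = 100% column needs an end-of-period report and a last-LDL endpoint. Every listed control is then above 55, so the control rate is 0% by construction. The q = 2% row matters because few controls may have a new LDL within 5 months; at f = 50% the rate is 3.2% against 2.9% with no screening, so inflation is almost nil.

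**Step 2: both arms are screened.** Intervention patients enter over time, and a candidate who reaches goal before the initial visit also fails entry. Apply the same formula to each arm, with a last-LDL endpoint:

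| q | Intervention f | Control f | Intervention rate | Control rate | False positives |
|---|---|---|---|---|---|
| 10% | 50% | 50% | 5.3% | 5.3% | 4.9% |
| 10% | 40% | 50% | 0.06/0.96 = 6.25% | 5.3% | 5.8% |
| 20% | 50% | 50% | 11.1% | 11.1% | 5.1% |
| 20% | 40% | 50% | 0.12/0.92 = 13.0% | 11.1% | 6.5% |

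The bias comes from the gap in timing between the arms. A report run after the period opens does not produce it by that fact alone.

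**Step 3: ever-reached or lowest-LDL endpoint.** A late report also admits patients who began at goal, had an in-period LDL below 55 and later rose above 55. They count as control successes. Let a be their number per control above 55 at the start. The intervention rate is again q, and the control rate is

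(q(1 − f) + a) / (1 − qf + a),

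which equals q when a = qf. At q = 10%, f = 50% the break-even is a = 0.05:

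| a per 100 | Control rate | False positives |
|---|---|---|
| 0 | 5.3% | 20% |
| 2.5 | 7.7% | 8% |
| 5 | 10.0% | 5% |
| 10 | 14.3% | 13% |
| 15 | 18.2% | 30% |

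In the last two rows nearly all false positives favour usual care.

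That break-even holds only if no listed patient was at goal solely before the period. Let b be the number of such patients per control above 55 at the start; they are listed and count as failures. Adding b to the denominator and setting the rate equal to q gives a = qf + qb/(1 − q). For q = 10%, f = 50%, b = 0.10: 0.05 + 0.01/0.9 = 0.061, or 6.1 per 100.

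**The case against.** The strongest reply is that no bias is shown. The run date is simply unstated. Controls are to have the same data as the intervention arm, which includes baseline lipids, and percent reduction needs a starting LDL, so judging eligibility before follow-up may well be intended. Intervention entry is itself spread over time, so a report run at about the time of those visits would screen both arms alike. And every q, f and a is assumed.

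Much of this stands. A reader might infer that the list is run late, because earlier referrals are excluded and the chart review is retrospective. The documents do not establish it: the exclusion shows only that some referrals come first, and the word retrospective describes the review of charts. A reader might also infer that any report run after the period opens is biased, or that the bias must favour the pharmacist arm. Steps 2 and 3 show that neither follows. The f = 100% column describes a comparison that would be meaningless on its face, and it should not carry the argument.

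What does not stand is that recording a baseline LDL settles the matter. The baseline panel is described only as recent, which is also undated, and chart review cannot restore patients whom the report has already dropped. The entry rule, followed literally in a late report, produces the selection described.

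**Conclusion.** The concern holds conditionally. Two gaps are plain in the text: the control LDL criterion has no index date, and the primary endpoint names no deciding LDL.

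- **Report late relative to intervention entry, last-LDL endpoint:** the control goal rate is too low and the pharmacist arm is favoured. Under the assumptions of step 1, with half of would-be control successes removed, false positives are about 11%, 20% and 33% at q = 5%, 10% and 20%.
- **Timing nearly matched (40% against 50% screened out):** about 6% at q = 10% and 6.5% at q = 20%.
- **Ever-reached or lowest-LDL endpoint:** the direction is uncertain.
- **Eligibility fixed before follow-up, or both arms screened at about the same time:** little or no bias from this source.

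The protocol does not let a reader tell which case applies. This should be fixed, because it decides who enters the comparator for the only outcome given a comparative test. It falls short of a demonstrated bias because it depends on an unstated run date.

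**What to change.** **Control Group.** Give each control an index date: either one fixed date at the start of the study period, or a date drawn from the intervention arm's initial-visit dates. Judge LDL > 55 on the last LDL on or before the index date for controls, and on or before the initial visit for intervention patients. State that later LDLs play no part in selection.

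**Report.** Build the SlicerDicer report on LDLs up to the index date, or run it without the LDL filter and apply the dated criterion at chart screening. Adding a date filter to a list already restricted to a current LDL > 55 cannot recover the dropped controls.

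**Primary endpoint.** Name the deciding LDL and its window, for example the last LDL within a stated number of days, identically in both arms and counted only after the index date or initial visit.

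**Cost.** Protocol wording, plus a modified query or somewhat more chart screening. No extra patients or visits.

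### The two arms are formed by different routes, so the unadjusted comparison mixes engagement and referral selection, of unknown size and uncertain direction, with the pharmacist effect

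*Combined protocol and SAP*

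**What the plan says.** All references are to the combined protocol and SAP.

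- **Intervention arm, source:** the section on Patient Identification states "Internal medicine providers and PharmDs will identify patients who are not meeting LDL goals for secondary prevention and could benefit from pharmacist intervention". The health-record reporting tool, SlicerDicer, is used "potentially for the intervention arm if referrals alone do not meet the sample size goal".
- **Intervention arm, start of care:** the section headed "In-person, initial visit" describes where pharmacist care begins.
- **Control arm, source (Control Group):** "Patients meeting inclusion criteria will be pulled from SlicerDicer", followed by "Patients included in the report will then be randomized and chosen for retrospective chart review".
- **Control arm, exclusion (Control Group):** "Any patients previously referred to the project by their provider will be excluded from the control group".
- **Consent (Informed Consent):** "Participants will be required to provide signed informed consent prior to inclusion in the study". The sentence does not name an arm.
- **Analysis (Statistical Analysis):** a t-test compares the arms on the primary outcome, LDL below 55 (yes/no). No matching, restriction or covariate adjustment is described. The goal is 75 patients per arm.

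**The concern.** The stated objective is to compare pharmacist interventions with usual care. That comparison needs arms that would have had similar goal attainment without the pharmacist. Here one arm is made up of people whom a clinician judged able to benefit, who accepted the project and who came to a visit. The other is a sample from a list, and may include people who had no contact with the clinic in the study months.

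Patients who attend and accept extra care may also be likelier to take their medication and to have blood drawn, and so to reach the goal under usual care. Conversely, clinicians may refer the patients who are hardest to bring to goal. Either mechanism would appear in the result as a pharmacist effect, or as the lack of one. The random step in the Control Group section does not help, because it selects charts within the control list and does not allocate patients between arms.

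**Working it through.** **1. The routes side by side**

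| Step | Intervention | Control |
|---|---|---|
| Source | Provider or pharmacist judgement; SlicerDicer as backup | SlicerDicer list |
| Link to clinic | Provider at a study clinic, LDL above 55 on record | Same inclusion criteria |
| Acceptance of the project | Needed in practice; signed consent for participants | Not stated; retrospective chart review |
| Visit in the study period | Care starts at an in-person visit | None required |
| Referred by provider, then declines | Not in this arm, if consent is a condition of entry | Barred without exception |

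No analysis step brings the two columns back together.

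**2. Size if only engagement differs**

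The documents give no goal-attainment or attendance rates, so there is no plan figure to reproduce. The target of 75 per arm cannot be reproduced either, because no alpha, power or rates are stated. All rates below are assumptions.

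Assume no pharmacist effect, an intervention arm made up only of attenders, and usual-care goal rates of 15% in attenders and 3% in non-attenders. Let *a* be the share of attenders among controls.

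Control rate = *a* × 15% + (1 − *a*) × 3%

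- *a* = 0.85: 12.75 + 0.45 = 13.2%; spurious difference 15 − 13.2 = 1.8 points
- *a* = 0.70: 10.5 + 0.9 = 11.4%; difference 3.6 points
- *a* = 0.50: 7.5 + 1.5 = 9.0%; difference 6.0 points

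**3. Sensitivity to the assumed rates**

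The same formula was run with 15%, 20% or 25% in engaged against 5% in non-engaged patients, and with 30% against 10%, each with 30%, 50% or 70% of controls engaged. The chance of a significant result was taken from a two-proportion z-test, 75 per arm, two-sided 0.05 (assumed):

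Φ((d − 1.96·SE0)/SE1) + Φ((−d − 1.96·SE0)/SE1),

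where d is the difference, SE0 uses the pooled rate and SE1 the separate rates.

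- Smallest: 15% against 5%, 70% engaged. Controls 12.0%, difference 3.0 points, rejection about 8%.
- Middle: 20% against 5%, 50% engaged. Controls 12.5%, difference 7.5 points, SE0 = 0.0602, SE1 = 0.0599, rejection about 24%.
- Largest: 25% against 5%, 30% engaged. Controls 11.0%, difference 14.0 points, rejection about 61%.

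Without selection the rejection rate is 5%.

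**4. The referral exclusion**

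Take the middle case and suppose that the exclusion removes a share *r* of engaged patients from the control pool. The engaged share becomes 0.5(1 − *r*) / [0.5(1 − *r*) + 0.5].

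- *r* = 0.25: engaged share 0.429, controls 11.4%, difference 8.6 points, rejection about 30%
- *r* = 0.50: engaged share 0.333, controls 10.0%, difference 10.0 points, rejection about 40%

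This assumes that those removed are engaged. Removing non-engaged decliners would work the other way.

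**5. Direction**

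In step 2 the bias vanishes if the selected patients' own usual-care rate equals the control rate (13.2%, 11.4% or 9.0%). If referral picks harder cases and their rate is lower than that, the bias runs against the intervention. The documents do not say which holds.

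**The case against.** The strongest case on the other side has five parts.

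- **Controls are not strangers to the clinic.** A reader might infer that they need no clinic contact at all. The documents do not support that. Controls need a primary care provider at a study clinic and an LDL on record, and the Exclusion Criteria remove inactive patients and those whose cholesterol is managed elsewhere. The Control Group section mentions only the inclusion criteria, but nothing says that the exclusions do not apply. What stands is that no visit during the study period is required.
- **Consent and attendance.** A reader might take consent to apply to the intervention arm alone. That is plausible for a chart review but is not stated. If controls also had to consent, the gap would narrow. Nor does any sentence remove a consented patient who misses the first visit from the intervention arm, since no analysis set is defined.
- **Loss from both arms.** A reader might infer that everyone who declines disappears. The rule bars only provider-referred patients. Those identified by a pharmacist or from the list who decline are not expressly barred from the control group. Keeping referred patients out of the comparator is also an ordinary safeguard against contamination.
- **Size.** The illustrated 1.8 to 6.0 points is small beside the noise. At 15% against 11.4%, the standard error is √(0.15·0.85/75 + 0.114·0.886/75) = 5.5 points. At two-sided 0.05, 75 per arm has 80% power only for differences of about 15 points (5% against 20.1%) to 22 points (30% against 52.4%). This is a fair caution, although bias adds to noise and does not average out.
- **Adjustment.** Comorbidities, insurance, initial treatment and follow-up appointments may be collected, with the same data recorded for controls. Adjustment could remove part of the confounding, but none is planned.

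**Conclusion.** The point holds in a limited form. The arms are selected differently, the planned comparison is unadjusted, and engagement and referral selection are therefore mixed with the pharmacist effect. Provider-referred patients who decline cannot be controls, and they are in neither arm if consent is a condition of entering the intervention arm.

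The size is unknown. Under the assumed rates, with no true effect and selection on engagement alone, the spurious benefit is 1.8 to 6.0 points in the main illustration and 3 to 14 points across the wider set, where the false-positive rate is about 8% to 61% instead of 5%. None of these rates comes from the documents.

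A reader might conclude that the bias must favour the pharmacist. The documents do not establish that: engagement would favour the intervention, while referral of harder cases could oppose it. An uncertain direction still leaves a result that cannot be read as the effect of the pharmacist alone. The plan should be changed, because much of the remedy is cheap.

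**What to change.** 1. **Align the controls.** State that the exclusion criteria apply to controls. Restrict controls to listed patients with a completed visit at their study clinic during the enrolment months. Use that visit as the index date, and the initial pharmacist visit as the index date in the intervention arm. Take baseline LDL before the index date and count outcome LDL only after it, over the same follow-up window in both arms. Without the index date, the visit filter would select controls on an event during follow-up.
2. **Use the random step for allocation where possible.** If SlicerDicer fills part of the intervention arm, randomly split the list into 'invite' and 'control'. Record each patient's source (referral or list). Report the list-sourced comparison separately, with all invited patients analysed as drawn whether or not they enrol, as far as chart review of non-enrolled invitees is permitted. Comparing only those who enrol would bring back the consent selection.
3. **Report and limit.** Give the number of referred or invited patients who did not enrol, and say whether the consent sentence covers controls. Limit the conclusion to an association among patients who attend and accept pharmacist care, because the visit filter does not remove consent or referral selection.

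**Cost:** a visit filter on the control report, an index date for each chart reviewed, one REDCap field for source, and a screening count. The control pool becomes smaller and represents patients in active contact with the clinic, not everyone on the list.
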